### Amendment 2 (03-Mar-2021)

#### Overall Rationale for the Amendment:

This amendment is considered to be non-substantial based on the criteria set forth in Article 10(a) of Directive 2001/20/EC of the European Parliament and the Council of the European Union because it neither significantly impacts the safety or physical/mental integrity of participants nor the scientific value of the study.

Section # and Name	Description of Change	Brief Rationale	Substantial/ Non-substantial
Section 1.1 Synopsis (Number of Participants)	Latest estimated date of last participant completed changed from Feb 2021 to May 2021	Revised to reflect latest estimated date	Non-substantial
Section 1.1 Synopsis (Statistical methods) Section 9.4.1 General Considerations Section 9.4.2.1 Primary Endpoint(s) Section 9.4.2.2 Secondary Endpoint(s) Section 9.4.2.3 Tertiary/Exploratory Endpoints	Mixed model repeated measures analysis changed to linear  Following text deleted: Normality assumptions will be tested and if warranted log-transformations will be done prior to performing the analysis  Addition of text as follows: and the ratio between them  Addition of 'and placebo versus 5 mg prednisolone' to the following text: The treatment comparisons of interest are the different doses of AZD9567 versus the different doses of prednisolone  Text regarding exploratory endpoints revised	For clarity	Non-substantial
Section 1.1 Synopsis and 9.5 Interim Analysis	Addition of second interim analysis and corresponding text revision	Progress decision	Non-substantial

Section # and Name	Description of Change	Brief Rationale	Substantial/ Non-substantial
Section 1.3 Schedule of Activities	Timepoint of serum cortisol, CCI [REDACTED] and ACTH samples clarified: For the MMTT a standardized mixed meal is to be provided around 07:00 on Day -1 and Day 4 (in each period). Serum cortisol, CCI [REDACTED] and ACTH are to be collected from the fasting MMTT blood samples, which is -15 minutes prior to the mixed meal on Days -1 and 4 (in each period)	To address discrepancy	Non-substantial
	Text in footnote m revised for clarity as follows: CGM will be performed during baseline (72h) and treatment period (72h), CGM/FGM will be fitted on Day -4 and removed on Day 4 (in each period) after assessments on Day 3 (in each period) are completed to ensure 2 continuous 72h monitoring periods covering baseline and treatment		
	Revision to clarify that all adverse events will be collected from time of signature of informed consent		
	Text revised to clarify that COVID-19 symptom telephone screening should be done prior to each visit, including Visit 6		
	Text included to clarify that fasting is not required for haematology and clinical chemistry on Day -2 (in each period)	To clarify fasting requirement on Day -2 (in each period)	
	Text revised that COVID-19 phone call will be done one day prior to visit	To clarify timepoint of COVID-19 phone call	
	Section 1.3 Schedule of Activities and Section 8.3.4 Clinical Safety Laboratory Assessments (Table 6)	Footnote added to SoA for cortisol, CCI [REDACTED] and ACTH to match footnote in Table 6 and included cortisol in footnote c in Table 6	

Section # and Name	Description of Change	Brief Rationale	Substantial/ Non-substantial
Section 1.3 Schedule of Activities and Section 9.4.3.1 Adverse Events	Text revised to clarify that adverse events after dosing and up to 21 days will be included in tables and that the adverse events occurring after 21 days will be listed separately Other minor revisions to this section	Consistency in AE follow-up for the 2 study periods	Non-substantial
Section 1.3.1 Blood Sampling Schedule for Mixed Meal Tolerance Tests (MMTTs)	Removed '(minutes)' in body of first column and add to heading of second column and abbreviation for FFAs added to footnote	Administrative change	Non-substantial
Section 1.1 Synopsis (Objectives and Endpoints Table) and Section 3 Objectives and Endpoints	CCI [REDACTED]	Aligning with the sampling points	Non-substantial
	Definition provided for $\Delta I_{10}/\Delta G_{10}$ , $\Delta I_{30}/\Delta G_{30}$ , $\Delta C_{10}/\Delta G_{10}$ , $\Delta C_{30}/\Delta G_{30}$ , HOMA-IR, and HOMA-S		
Section 4.1.1 Order of Assessments	Text revised as follows: Safety ECG and vital signs (systolic and diastolic BP, pulse rate) should be taken pre-dose and approximately 1.5 hours after IMP dosing on Days 1 and 28 and corresponding time on Days 4 and 31	To address discrepancy	Non-substantial
	Text revised to clarify aural body temperature should be taken and timing of ECG assessments		
Section 5.1 Inclusion Criteria	Text for contraception requirement revised	To address discrepancy	Non-substantial
	Clarification that Inclusion Number 2 refers to fasting plasma glucose	To correct error	
Section 5.2 Exclusion Criteria	Text revised to clarify that one rescreening per participant is allowed Addition of following: COVID-19 vaccine (regardless of vaccine delivery platform, eg, vector, lipid nanoparticle) 30 days prior to the date of randomisation (from last vaccination or booster dose)	To clarify rescreening and addition of COVID-19 vaccination criterion	Non-substantial
Section 5.3.1 Meals and Dietary Restrictions	Text revised to clarify that overnight fasting is required prior to each dosing, ie, 12 hours prior and 30 minutes after dosing	To clarify fasting requirement for study intervention dosing	Non-substantial

Section # and Name	Description of Change	Brief Rationale	Substantial/ Non-substantial
	Fasting requirement added for ACTH	To clarify fasting requirement for ACTH	
Section 6.2 Preparation/ Handling/ Storage/ Accountability of Interventions	Text included to clarify that participants should receive the oral suspension first, followed by the capsules	To clarify order of IMP intake	Non-substantial
Section 6.5 Concomitant Therapy	Following text added: If a patient is being considered for enrolment into the study and also being considered for COVID-19 vaccination, the patient must not be randomised until at least 30 days after the last dose of vaccine or booster.	To clarify COVID-19 vaccination in relation to study randomisation.	Non-substantial
Section 7.1 Discontinuation of Study Intervention	Text corrected as follows: FPG > 12 mmol/l (216mg/dL)	To correct conversion error	Non-substantial
	COVID-19 vaccination related discontinuation requirement added	To clarify COVID-19 vaccination related participant discontinuation	
Section 8 Study Assessments and Procedures	Blood volume collected from each participant during the study changed from 500 mL to 600 mL and the following text deleted: including any extra assessments that may be required	For consistency with the blood volume noted in consent form	Non-substantial
Section 8.2.2 Mixed Meal Tolerance Test (MMTT)	Text added to clarify that the solid mixed meal should be consumed as fast as the participant can, within 30 minutes	To clarify requirement for completing mixed meal	Non-substantial
CCI [REDACTED]	CCI [REDACTED]	Aligning with the sampling points	Non-substantial
Section 9.1 Statistical Hypotheses	Bullet points added for inclusion of Cohort 2 and Cohort 3	For better clarity	Non-substantial
	Addition of following text: Cohorts 2 and 3 are not powered, thus all significance testing should be considered exploratory		

Section # and Name	Description of Change	Brief Rationale	Substantial/ Non-substantial
Section 9.2 Sample Size Determination	Text regarding significance testing and presentation of Cohorts 2 and 3 results revised	For better clarity	Non-substantial
Section 9.3 Populations for Analyses	Definition of analysis sets updated	To reflect latest definitions as per the statistical analysis plan	Non-substantial
Section 9.4 Statistical Analyses	The following text deleted: be finalised prior to first participant in and it will	For better clarity	Non-substantial
Section 9.4.2.1 Primary Endpoint(s)	
Addition of following: The following comparison will be performed:
 
 
• 72 mg AZD9567 versus 40 mg prednisolone (Cohort 1).
 
• 40 mg AZD9567 versus 20 mg prednisolone (Cohort 2).
 
• Placebo versus 5 mg prednisolone (Cohort 3).
 
 
Deletion of following: Normality assumptions will be tested and, if warranted, log transformations will be done prior to performing the analysis. Further details will be provided in the SAP.
 
Text revised from “Should there be more than 10% of participants erroneously treated, a sensitivity analysis will be performed using the actual treatment received.” To “Should there be more than 10% of participants erroneously treated, a sensitivity analysis will be performed on the per protocol set.”
	For better clarity	Non-substantial
Section 9.4.2.2 Secondary Endpoint(s)	Text regarding analysis methods updated	For better clarity	Non-substantial
Appendix F	Addition of COVID-19 related restriction	To clarify COVID-19 vaccination related restriction	Non-substantial
Appendix H Protocol Amendment History	Amendment history for previous version moved to Appendix H	For consistency with latest template	Non-substantial

Section # and Name	Description of Change	Brief Rationale	Substantial/ Non- substantial
Global	Minor editorial corrections (typos, formatting, etc)	Document quality	Non-substantial

# 1           **PROTOCOL SUMMARY**

## 1.1          **Synopsis**

**Protocol Title: A Phase 2a Randomised, Double Blind, Multi-centre Study to Assess the Effect on Glucose Homeostasis of Two Dose Levels of AZD9567, Compared to Prednisolone, in Adults with Type 2 Diabetes**

**Short Title:** Phase 2a, Randomised, Double Blind, Multi-centre Study to Assess the Effect on Glucose Homeostasis of Two Dose Levels of AZD9567, Compared to Prednisolone, in Adults with Type 2 Diabetes

### **Rationale:**

AZD9567 is a glucocorticoid receptor (GR) modulator that shows promising separation between anti-inflammatory and dysglycaemic effects in preclinical studies and in two dose escalation studies in healthy volunteers (D6470C00001 and D6470C00002). In addition, in a study in patients with active rheumatoid arthritis (RA) (D6470C00003), 40 mg AZD9567 resulted in a similar profile in term of efficacy effects to prednisolone 20 mg following 14 days of once daily dosing. The aim of this study is to assess the effect on glycaemic control of AZD9567 as compared to prednisolone in a more relevant patient population.

The doses used (40 mg AZD9567 [equipotent to 20 mg prednisolone] and 72 mg AZD9567 [equipotent to 40 mg prednisolone]) were chosen based on studies D6470C00001 and D6470C00002 (equipotency was based on ex-vivo lipopolysaccharide [LPS] stimulated tumour necrosis factor alpha [TNF $\alpha$ ] release in whole blood). In study D6470C00002, the effect of several doses of AZD9567 up to 80 mg (equipotent to 45 mg prednisolone) on plasma glucose was investigated and compared with prednisolone. After an oral glucose tolerance test (OGTT) the area under the concentration-time curve from 0 to 4 hours post-dose, AUC(0-4), was measured. The result showed that the effect of AZD9567 80 mg on glucose was similar to the lower dose of 5 mg prednisolone despite being equipotent to 45 mg prednisolone.

This is a randomised, double blind, multi-centre, double dummy, two-way cross-over study to assess the effect on glycaemic control of AZD9567, as measured by the glucose AUC(0-4) versus baseline following a standardised mixed meal tolerance test (MMTT), compared to prednisolone in adults with type 2 diabetes mellitus (T2DM). This study will also evaluate the safety, tolerability, and pharmacokinetics (PK) of AZD9567.

## Objectives and Endpoints

Objectives	Endpoints/Outcome Measures
Primary	

 
To determine the pharmacodynamic (PD) effect of AZD9567 on glucose homeostasis compared to prednisolone
 
	
 
Primary endpoint: Change in glucose AUC(0-4) versus baseline compared to prednisolone following a standardised mixed meal tolerance test (MMTT)
 

Secondary	

 
To determine the effect of AZD9567 on continuous glucose monitoring (CGM) compared to prednisolone
 
	
 
Mean daily glucose at 48 - 72 hours treatment as determined from multiple measures via the CGM system
 
Rise in mean daily glucose over 24-hour periods from start of investigational medicinal product (IMP) dosing (0 - 24 hours, 24 - 48 hours, 48 - 72 hours)
 

 
To determine the PD effect of AZD9567 following a MMTT compared to prednisolone
 
	
 
Change from baseline in fasting glucose
 
Change from baseline AUC(0-4) on hormones related to glucose homeostasis (insulin, glucagon, glucagon-like peptide-1 [GLP-1], glucose-dependent insulin releasing polypeptide [GIP]) and free fatty acids (FFAs)
 

 
To determine the PD effect of AZD9567 on glucose homeostasis through an MMTT in comparison to prednisolone
 
	
 
Change from baseline in AUC(0-4) on insulin and C-peptide
 

 
To determine the PD effect of AZD9567 on derived measures of beta cell function from the MMTT compared to prednisolone
 
	
 
MMTT derived first phase insulin response (<math>\Delta I_{10}/\Delta G_{10}</math>, <math>\Delta I_{30}/\Delta G_{30}</math>, <math>\Delta C_{10}/\Delta G_{10}</math>, <math>\Delta C_{30}/\Delta G_{30}</math> – where, <math>\Delta</math>: change from baseline, I: insulin, C: C-peptide, G: glucose)
 
Homeostatic model assessment of insulin resistance (HOMA IR),
 

	homeostatic model assessment of insulin sensitivity (HOMA S)

 
To determine the effect of AZD9567 on urinary sodium (U-Na) and urinary potassium (U-K) excretion compared to prednisolone
 
	
 
24-hour sodium and potassium concentration
 

 
To evaluate the PK of AZD9567 following once daily dosing
 
	
 
Plasma PK parameters
 

 
To collect plasma samples for analysis of prednisolone. Reported outside the CSR
 
	
 
Plasma concentrations of prednisolone
 

 
To explore the relationship between AZD9567 exposure and inhibition of LPS-stimulated TNF<math>\alpha</math> release for high and low dose comparison (Cohort 1 and Cohort 2)
 
	
 
TNF<math>\alpha</math> concentrations
 

Safety Objectives	

 
To evaluate the safety and tolerability of AZD9567 compared to prednisolone
 
	
 
Adverse events (AEs)/Serious adverse events (SAEs)
 
Vital signs
 
Electrocardiograms (ECGs)
 
Changes in clinical chemistry/haematology parameters
 
Morning serum cortisol
 
Adrenocorticotrophic hormone (ACTH)
 

For Tertiary/Exploratory objectives and outcome measures, see Section 3 of the Clinical Study Protocol (CSP).

### Overall Design

This is a randomised, double blind, multi-centre, double dummy, two-way cross-over study with the primary objective of determining the effect of AZD9567 on glucose homeostasis (ie, glycaemic control) versus a dose of prednisolone expected to deliver similar anti-inflammatory effects, as assessed by the change in glucose AUC following the standardised MMTT compared to baseline. Approximately 46 participants with T2DM will be randomised into the study, which will be conducted in Germany.

AZD9567 will be administered once daily as an oral suspension at two dose levels (40 mg/day and 72 mg/day). Prednisolone capsules will be administered orally at three different dose levels (5 mg/day, 20 mg/day, and 40 mg/day). There will be three separate, two-way cross-over cohorts, with three different dose combinations (72 mg AZD9567/40 mg prednisolone, 40 mg AZD9567/20 mg prednisolone, and placebo/5 mg prednisolone). Since the investigational medicinal product (IMP) has different formulations, it will be administered in a double dummy fashion, with each participant taking both oral suspension and capsules of prednisolone/placebo.

Participants who meet all eligibility criteria will be randomised in a ratio of 1:1 to a cohort and sequence group as shown in the Cohorts and Duration section below.

**Disclosure Statement:** This is a cross-over study with three separate two-way cross-over sequence groups that is participant and investigator blinded.

**Number of Participants:**

Approximately 46 participants will be randomly assigned to study intervention with a view to achieve 40 evaluable participants completing the study.

Study period		Phase of development
Estimated date of first participant enrolled	Sep 2020	Phase 2a
Estimated date of last participant completed	May 2021	Phase 2a

**Cohorts and Duration:**

There will be three dose comparisons, each in a separate two-way cross-over:

- **Cohort 1:** participants will be randomised in a ratio of 1:1 to receive AZD9567 and prednisolone over two 72-hour periods in a cross-over design (72 mg AZD9567 followed by 40 mg prednisolone [AB sequence group] or 40 mg prednisolone followed by 72 mg AZD9567 [BA sequence group]). There will be a 3-week washout period between treatment periods. (N=24 completed [12 in each sequence group].)
- **Cohort 2:** participants will be randomised in a ratio of 1:1 to receive AZD9567 and prednisolone over two 72-hour periods in a cross-over design (40 mg AZD9567 followed by 20 mg prednisolone [AB sequence group] or 20 mg prednisolone followed by 40 mg AZD9567 [BA sequence group]). There will be a 3-week washout period between treatment periods. (N=8 completed [4 in each sequence group].)
- **Cohort 3:** participants will be randomised in a ratio of 1:1 to receive placebo and prednisolone over two 72-hour periods in a cross-over design (placebo followed by 5 mg prednisolone [AB sequence group] or 5 mg prednisolone followed by placebo [BA

sequence group]). There will be a 3-week washout period between treatment periods. (N=8 completed [4 in each sequence group].)

Participants will be expected to take part in the study (from screening to follow-up) for 79 days; the study duration may be extended for screening and washout (see Schedule of Assessments [SoA] in Section 1.3).

### **Statistical methods**

For Cohort 1, with a total sample size of 24 participants we can detect an absolute difference of 10% change from baseline in glucose AUC(0-4) (mmol/L 4h), ie, a difference of ~134 mmol/L 4h between prednisolone and AZD9567, with a power of 80% and significance level of 0.05, 1-sided test. Withdrawn participants should be replaced to ensure that 24 participants are evaluable (12 in each sequence group).

The primary PD variable, change from baseline in glucose AUC(0-4) following a standardised MMTT, will be analysed using a linear mixed model with baseline included as covariate. Treatment, period and sequence will be included as fixed effects with participant within sequence as random effect. Models will be run separately for each cohort. Should there be more than 10% of participants erroneously treated, a sensitivity analysis will be performed using the actual treatment received instead. Descriptive statistics and graphical presentations will be presented.

Mean daily glucose measured by continuous glucose monitoring (CGM) is a secondary endpoint and will be analysed using a MMRM analysis with baseline as covariate. Treatment, period and sequence will be included as fixed effects, participant within sequence as random effect and day as repeated measure. Models will be run separately for each cohort. Similar analyses will be performed for the rise in mean daily glucose over 24-hour periods. Fasting glucose as derived from the baseline measure in the MMTT, change in hormones related to glucose homeostasis in response to MMTT (insulin, glucagon, GLP-1, glucose-dependent insulin releasing polypeptide [GIP]), changes in FFAs during MMTT, HOMA-IR, HOMA-S, and 24-hour U-Na and U-K excretion and the ratio between them will be analysed in a similar way to the primary PD endpoint.

Safety will be assessed by descriptive analysis of adverse events (AEs)/serious AEs (SAEs), vital signs, ECGs, clinical laboratory assessments (clinical chemistry/haematology), morning serum cortisol, and adrenocorticotrophic hormone (ACTH).

Continuous data will be summarised using descriptive statistics (number of observations, mean, standard deviation, median, 25th and 75th percentiles [where appropriate], minimum and maximum). For log-transformed data it is more appropriate to present geometric mean, geometric coefficient of variation, median, minimum, and maximum. Frequencies and percentages will be used for summarising categorical (discrete) data. Time parameters (tmax,

tlast, etc) will be presented as minimum, median, and maximum only. Confidence intervals and p-values, when presented, will generally be constructed at the 2-sided 95% level. Unless otherwise stated, summaries will be presented by cohort and treatment. The treatment comparisons of interest are the different doses of AZD9567 versus the different doses of prednisolone and placebo versus 5 mg prednisolone. No formal comparisons between the different AZD9567 doses will be conducted. Similarly, no formal comparisons between the different prednisolone doses will be conducted.

The primary analysis population for pharmacodynamics will be the full analysis set. The primary analysis population for safety will be the safety analysis set. The PK analysis set will include all participants who received at least one dose of study intervention and for whom there is at least one reportable PK concentration, no important protocol deviations, or AEs considered to have an effect upon PK.

Two interim analyses are planned to evaluate the feasibility of the assumptions and conduct sample size re-estimation if required (see Section 9.5).

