##### **Type of Participant and Disease Characteristics**

- 2 Participants with diagnosis of T2DM for 6 months prior to screening: HbA1c in the diabetes range or fasting plasma glucose 126 -220 mg/dL.
- 3 On stable metformin therapy for at least 4 weeks, where no significant dose change (increase or decrease  $\geq$  500 mg/day) has occurred prior to screening and HbA1c 6% – 9.5%, or on dual therapy with metformin in combination with SGLT2i or DPP4i and HbA1c 6% – 8%. Participants on dual therapy will require 2 weeks washout of SGLT2i or DPP4i.
- 4 Venous access suitable for multiple cannulations.

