4.2 General Presentation Considerations

Summary tables will include the results of each planned sequence in the case of the all randomised subjects set (RND), planned treatment in the case of the Full Analysis Set (FAS) or actual treatment in the case of the Safety Analysis Set (SAF), Per Protocol Analysis Set (PP) and the PK Analysis Set (PKAS).

Non-PK continuous data will be summarised in terms of number of observations, the mean, standard deviation (SD), median, 25th and 75th percentiles (where appropriate), minimum, maximum. In the

case of PK data, the Pharmacokinetics section of this SAP lists the statistics included in the summary tables.

For continuous data, the mean, median and geometric mean will be rounded to one additional decimal place compared to the original data. The SD and geometric coefficient of variation (CV) will be rounded to two additional decimal places compared to the original data. Minimum and maximum will be displayed with the same accuracy as the original data. The maximum number of decimal places reported will be four for any summary statistic.

One decimal will be presented for the geometric CV % included in the PK summary tables.

Categorical data will be summarised in terms of the number of participants, frequency counts and percentages.

Percentages will be presented to one decimal place. Percentages will not be presented for zero counts. Percentages will be calculated using n as the denominator (participants included in the analysis sets or number of non-missing values).

Confidence intervals (CIs) will be presented to one additional place than the original data. P-values greater than or equal to 0.001, in general, will be presented to three decimal places. P-values less than 0.001 will be presented as “<0.001”.

Unless otherwise noted, for the calculation of a change from baseline, the last reliable assessment (in the case of blood pressure, the average of triplicate assessments) prior to the first dose of each study treatment will be considered the baseline measurement.

In the case of assessments at scheduled timepoints, the post-baseline scheduled or non-scheduled reliable assessment closest to the timepoint will be used. If two post-dose assessments are equidistant from a timepoint, the earlier of the two will be used.

All glucose values will be presented in mmol/L. The following formula will be used for the conversion of glucose concentrations from mg/dL to mmol/L:

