The calculation of the change in glucose, insulin, C-peptide GLP-1, GIP, glucagon and FFAs AUC(0-4) will involve the following steps:

1. The AUC(0-4) each day when the MMTT is consumed will be calculated by means of the linear-log trapezoidal method, i.e., using the linear trapezoidal method when concentrations are increasing and the logarithmic trapezoidal method when concentrations are decreasing.

Accordingly, for a given time interval ($t_1 - t_2$), the AUC could be calculated as follows:

i) by the linear trapezoidal method:

$$AUC = 1/2 (C_1 + C_2) (t_2 - t_1)$$

ii) by the logarithmic trapezoidal method:

$$AUC = [(C_1 - C_2) / (\ln(C_1) - \ln(C_2))] (t_2 - t_1)$$

where:

CCI [REDACTED]

- C_1 and C_2 are the concentrations at times 1 (t_1) and 2 (t_2).the first time interval ($t_1 - t_2$) is equal to t_1 (ie, the concentration at -15 minutes is assumed to be the same as if it had been made at 0 minutes),
- for assessments at 10, 20, 30, 60, 75, 120 and 180 minutes, t_1 and t_2 are actual times,
- for the planned assessment at 240 minutes, the planned time (240) will be used if such an assessment has been performed within the allowed time window (± 5 minutes).

The total AUC between 0 and 240 minutes will be calculated as the sum of the AUC for each of the intervals described in i) and ii).

The total AUC between two time points will be calculated as the sum of the AUCs calculated for each of the intervals between the two time points.

2. The change in AUC(0-4) will be calculated as:

$$\Delta \text{AUC}(0-4) = \text{AUC}(0-4) \text{ at Day 4} - \text{AUC}(0-4) \text{ at Day -1}$$

For the calculation of MMTT $\text{AUC}_{0-4\text{hr}}$, the pre-meal measurement (at -15 min) value will be treated as the value at the meal time (0 minutes). The actual time span for each post-meal measure will be calculated starting from the meal time (0 minutes). If any actual sample collection times are missing, use the scheduled nominal times with reference to the actual meal time to impute.

If the actual sampling times differ from the nominal times more or equal to $|5|$ min, this will be deemed on case-by-case basis if should be considered protocol deviation.

If greater than 50% of scheduled measures are missing, the AUC will be set as missing; if the first two or last two scheduled measures are both missing, then the AUC will also be set as missing; otherwise:

For all the MMTT endpoints (glucose, insulin, glucagon, GLP-1, GIP, FFAs and C-peptide):

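### The Cohort 1 target is stated both as 10% and as about 134 mmol/L 4h, and the two agree only at a baseline AUC that is implausible as a mean for this type 2 diabetes population

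*Protocol*

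**What the plan says.** The visible power statement is in the Statistical methods part of the protocol synopsis (Section 1.1). For Cohort 1, the only powered cohort, it gives the target in these words: "we can detect an absolute difference of 10% change from baseline in glucose AUC(0-4) (mmol/L 4h), ie, a difference of ~134 mmol/L 4h". The comparison is prednisolone against AZD9567, and the test conditions attached to that target are "with a power of 80% and significance level of 0.05, 1-sided test". On dropouts the same paragraph adds: "Withdrawn participants should be replaced to ensure that 24 participants are evaluable (12 in each sequence group".

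Three other places bear on what those figures can mean:

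- **Eligibility** (protocol 5.1). Criterion 2 asks for "HbA1c in the diabetes range or fasting plasma glucose 126 -220 mg/dL". Criterion 3 sets the HbA1c window for metformin alone: "has occurred prior to screening and HbA1c 6% – 9.5%, or on dual therapy with metformin", where the dual-therapy window is 6% to 8%.
- **Units** (SAP 4.2). "All glucose values will be presented in mmol/L", with 0.0555 as the factor from mg/dL.
- **AUC derivation** (SAP 4.12.2). "The total AUC between 0 and 240 minutes will be calculated as the sum of the AUC for each of the intervals". Sampling times are in minutes, and no AUC unit is given.

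The sample-size text in protocol 9.2 and SAP 4.14 is redacted, so the reference baseline, the SD and their source cannot be seen.

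**The concern.** The synopsis presents 10% and 134 as one effect. That is true at a single baseline value, and the value does not look like a post-meal AUC in people with type 2 diabetes. The unit as printed does not help: it is a concentration followed by a duration, and reading it literally in hours gives an impossible figure.

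The power claim is at stake. If the planning baseline is too low for this population, the two targets separate, and 80% can describe at most one of them unless something else compensates. A reader cannot tell which one the sponsor meant. The first interim analysis (protocol 9.5, SAP 4.12.1.3) is there to check the planning assumptions and re-estimate the sample size if needed, so an ambiguous target leaves that check without a clear yardstick.

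**Working it through.** **Inputs.** From the synopsis: target 10% and ~134, n = 24, one-sided alpha 0.05, power 80%. From protocol 5.1: fasting glucose 126 to 220 mg/dL. From SAP 4.2: factor 0.0555. From SAP 4.12.2: AUC over 240 minutes. From protocol 5.3.1, Tables 3 and 4: a test meal with about 75 g carbohydrate.

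**Step 1: the baseline that makes the two figures agree.** 134 / 0.10 = 1340.

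- In hours: 1340 / 4 = 335 mmol/L mean glucose, and 134 / 4 = 33.5 mmol/L mean difference. Not possible.
- In minutes: 1340 / 240 = 5.58 mmol/L mean glucose (5.58 / 0.0555 ≈ 101 mg/dL), and 134 / 240 = 0.56 mmol/L mean difference. Physiologically possible.

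So the figure only makes sense in mmol·min/L.

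**Step 2: compare with the trial's own glucose range.** 126 × 0.0555 = 6.99 mmol/L and 220 × 0.0555 = 12.21 mmol/L. A profile that stayed flat at those values for four hours, with no rise after the meal, gives AUC(0-4) of 6.993 × 240 = 1678 and 12.21 × 240 = 2930 mmol·min/L. Both exceed 1340.

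**Step 3: how far apart the targets are.** These baseline means are illustrations, not figures from the plan.

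| Baseline mean (mmol/L) | AUC(0-4) (mmol·min/L) | 10% of it | 134 as % of it |
|---|---|---|---|
| 5.58 (implied) | 1340 | 134 | 10.0% |
| 6.99 | 1678 | 168 | 8.0% |
| 9.99 | 2398 | 240 | 5.6% |
| 12.21 | 2930 | 293 | 4.6% |

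**Step 4: what this could do to power.** The 80% cannot be reproduced, because the SD is redacted. Instead, take the 80% as given for 134 and solve for the SD of the paired difference. Power = P(T > t[0.95, 22]), where T is noncentral t with 22 df and noncentrality δ√24 / SD. Setting δ = 134 and power = 0.80 gives SD ≈ 256, about 19% of 1340. The normal formula, 134 × √24 / (1.645 + 0.842), gives about 264. Two scenarios follow, all one-sided at 0.05 with n = 24:

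- **SD proportional to AUC.** SD = 256 × AUC / 1340. The 10% target keeps 80% at every baseline. The 134 target has 63% at 6.99 mmol/L, 40% at 9.99 and 31% at 12.21.
- **SD fixed at 256.** The 134 target keeps 80%. The 10% target has 93% at 6.99 mmol/L and over 99% at 9.99 and 12.21.

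**The case against.** The strongest reply is that this is a labelling problem. Each target can be defined on its own: 134 mmol·min/L is a mean difference of 0.56 mmol/L, and a percentage effect is what the SAP's log-scale model estimates. In each scenario above, one of the two stated targets keeps exactly the stated power, and the direction of any error in the other is open. The SD of 256 comes from the very 80% under question. Neither 134 nor 10% enters the endpoint derivation, the models or the confidence intervals. All of this stands, and it limits the point to the planning statement.

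A reader might infer several stronger things that the documents do not support:

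- **That no eligible participant could have this baseline.** Criterion 2 is an either/or. Entry by HbA1c sets no fasting-glucose floor, and criterion 3 admits HbA1c from 6%. An individual mean near 5.6 mmol/L is not excluded; it is implausible only as a cohort mean.
- **That the unit is impossible, or the power refers to nothing.** The minute reading gives a sensible quantity, so the unit is mislabelled. The power statement is ambiguous and cannot be checked, which is not the same as void.
- **That 1340 came from a non-diabetic study.** The SAP reference list includes a trial in men with the metabolic syndrome, but nothing visible links it to this figure.
- **That the sample-size section is deficient, or that the first interim used the wrong target.** The section is redacted and may state the baseline and SD. No visible text says which target any re-estimation used, and the SAP revision history already records changes made during that interim.

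Redaction does not rescue the synopsis sentence itself: hidden text cannot make 134 equal 10% of anything other than 1340.

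**Conclusion.** The synopsis sentence is wrong as written for this trial's population. Its two versions of the target effect coincide only in mmol·min/L at a baseline four-hour mean of about 5.6 mmol/L, below the protocol's fasting range even before any rise from the meal. At baseline means of 7.0 to 12.2 mmol/L, a true 10% is about 1.25 to 2.2 times the stated 134 (168 / 134 and 293 / 134), so 80% power cannot in general belong to both.

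The arithmetic in steps 1 to 3 rests on the documents plus the illustrative baselines. The power figures rest further on the back-solved SD and on how it scales. They show the possible spread; they do not estimate the trial's actual power.

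**What to change.** In the synopsis, and in the sample-size sections if they carry the same figures:

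1. Give the absolute target in mmol·min/L, or convert it (134 / 60 = 2.23 mmol·h/L), and state the same unit for the AUC in SAP 4.12.2.
2. Say whether the 80% power refers to the 10% difference or to the absolute difference.
3. State a type 2 diabetes baseline AUC(0-4) and recompute the other figure from it.
4. Restate the power for n = 24, with the SD on the same scale, if it changes.
5. Use the reconciled target wherever the planning assumptions are assessed, including any account of the first interim analysis.

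The cost is one recalculation and a few lines of text. No change to the endpoint, the models or data collection is needed. The restated power or percentage may be less favourable than the current sentence suggests.
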